### 4.1. Protocol Deviations

Important protocol deviations (including deviations related to study inclusion/exclusion criteria, conduct of the trial, patient management or patient assessment) will be summarised and listed.

Protocol deviations will be tracked by the study team throughout the conduct of the study in accordance with the Protocol Deviation Management Plan (PDMP) 25-Sep-2018 Version 001. See Section [10.1](#) for further details.

A separate summary and listing of all inclusion/exclusion criteria deviations will also be provided. This summary will be based on data as recorded on the inclusion/exclusion page of the eCRF.

## 5. CONSIDERATIONS FOR DATA ANALYSES AND DATA HANDLING CONVENTIONS

### 5.1. Study Treatment & Sub-group Display Descriptors

Treatment Group Descriptions			
RandAll NG		Data Displays for Reporting	
Code	Description	Description	Order in TLF
Part A			
A	GSK2982772 120mg minitab MR RR1 oral single dose	MT-12h 120mg Fasted	2
B	GSK2982772 120mg minitab MR RR2 oral single dose	MT-8h 120mg Fasted	3
C	GSK2982772 120mg IR oral single dose	IR 120mg Fasted	1
D	GSK2982772 120mg minitab MR RR3 oral single dose	MT-12h 120mg Fed (Standard)	4
E	GSK2982772 120mg minitab MR RR4 oral single dose	n/a	5
F	GSK2982772 120mg minitab MR fed state	n/a	6
Part B			
G	GSK2982772 minitab MR Repeat Dose 1	MT-12h 120mg Fasted	1
H	GSK2982772 minitab MR Repeat Dose 2	MT-12h 240mg Fasted	2
J	GSK2982772 minitab MR Repeat Dose 3	MT-12h 300mg Fed (Standard)	3
Part C			
K	GSK2982772 240mg (matrix monolithic) MR oral single dose	MM-12h 240mg Fasted	2
L	GSK2982772 240mg IR oral single dose	IR 240mg Fasted	1
M	GSK2982772 360mg or 480mg (matrix monolithic) MR oral single dose	MM-12h 480mg Fasted	3
N*	GSK2982772 240mg (matrix monolithic) MR fed state	MM-12h 480mg Fed (Standard)	4
P	GSK2982772 360mg or 480mg (matrix monolithic) MR delayed fed (standard meal) or fed (high-fat meal)	MM-12h 480mg Delayed Fed (Standard)	5
Q	GSK2982772 dose tbd (matrix monolithic) MR QD or BID prandial state tbd.	MM-12h 240 mg Delayed Fed (High-Fat)	6

\* The randomization description for Period 4 of Part C (code N) indicates 240 mg, but the label has been updated to 480 mg to reflect the actual treatment administered.

## 5.2. Baseline Definitions

For all endpoints (except as noted in baseline definitions) the baseline value will be the latest pre-dose assessment with a non-missing value, including those from unscheduled visits. If time is not collected, Day 1 assessments are assumed to be taken prior to first dose and used as baseline.

Parameter	Study Assessments Considered as Baseline			Baseline Used in Data Display
	Screening	Day -1	Day 1 (Pre-Dose)	
Safety				
Vital signs	X	X	X	Day 1 (Pre-Dose)
12-lead ECG	X	X	X	Day 1 (Pre-Dose)
Laboratory (Haematology, clinical chemistry and urinalysis)	X	X	X	Day 1 (Pre-Dose)

Unless otherwise stated, if baseline data is missing no derivation will be performed and baseline will be set to missing.

## 5.3. Other Considerations for Data Analyses and Data Handling Conventions

Other considerations for data analyses and data handling conventions are outlined in the appendices:

Section	Component
10.3	Appendix 3: Assessment Windows
10.4	Appendix 4: Study Phases and Treatment Emergent Adverse Events
10.5	Appendix 5: Data Display Standards & Handling Conventions
10.6	Appendix 6: Derived and Transformed Data
10.7	Appendix 7: Reporting Standards for Missing Data
10.8	Appendix 8: Values of Potential Clinical Importance

## 6. STUDY POPULATION ANALYSES

### 6.1. Overview of Planned Study Population Analyses

The study population analyses will be based on the Safety population, unless otherwise specified.

Study population analyses including analyses of subject's disposition, protocol deviations, demographic and baseline characteristics, prior and concomitant medications, and exposure and treatment compliance will be based on GSK Core Data Standards. Details of the planned displays are presented in [Appendix 11: List of Data Displays](#).

## 7. SAFETY ANALYSES

The safety analyses will be based on the Safety population, unless otherwise specified.

### 7.1. Adverse Events Analyses

Adverse events analyses including the analysis of adverse events (AEs), Serious (SAEs) and other significant AEs will be based on GSK Core Data Standards. The details of the planned displays are provided in [Appendix 11: List of Data Displays](#).

### 7.2. Clinical Laboratory Analyses

Laboratory evaluations including the analyses of Chemistry laboratory tests, Hematology laboratory tests, Urinalysis, and liver function tests will be based on GSK Core Data Standards. The details of the planned displays are in [Appendix 11: List of Data Displays](#).

In addition to GSK Core Data Standards, Lipids (Total Cholesterol and Triglycerides) outside the normal range will be summarised. Other Safety Analyses

The analyses of non-laboratory safety test results including ECGs and vital signs will be based on GSK Core Data Standards, unless otherwise specified. Suicide risk monitoring including analyses of Colombia Suicide Severity Rating Scale (C-SSRS) and Possible Suicidality Related Adverse Event (PSRAE) will be based on GSK Core Data Standards, unless otherwise specified. The details of the planned displays are presented in [Appendix 11: List of Data Displays](#).

## 8. PHARMACOKINETIC ANALYSES

### 8.1. Primary Pharmacokinetic Analyses – Part A (Periods 1 – 3) and Part C (Periods 1 & 2)

#### 8.1.1. Endpoint / Variables

##### 8.1.1.1. Drug Concentration Measures

Refer to [Appendix 5](#): Data Display Standards & Handling Conventions (Section [10.5.2](#) Reporting Standards for Pharmacokinetic)

##### 8.1.1.2. Derived Pharmacokinetic Parameters

Pharmacokinetic parameters will be calculated by standard non-compartmental analysis according to current working practices and using the currently supported version of WinNonlin . All calculations of non-compartmental parameters will be based on actual sampling times. Pharmacokinetic parameters listed will be determined from the plasma concentration-time data, as data permits.

Parameter	Parameter Description
Parts A and C Relative Bioavailability of MR vs IR	
AUC (0-inf)	Area under the curve from time zero to infinity
AUC (0-t) 	Area under the curve from time zero to the last quantifiable concentration
AUC (0-24)	Area under the curve from time zero to 24 hours
AUC (0-12) 	Area under the curve from time zero to 12 hours,
AUC%extrap	Percentage of AUC extrapolated beyond the last measured time point.
t 1/2	Terminal half-life
T lag	Time from dosing to first quantifiable concentration.
T max	Time of maximum observed concentration
C max	Maximum observed concentration
C 24h	Concentration at 24 hours post-dose
C 12h 	Concentration at 12 hours post-dose
C max :C 12h 	Ratio of maximum and 12 hour concentrations
C max :C 24h	Ratio of maximum and 24 hour concentrations

#### NOTES:

- Additional parameters may be included as required.
- No log transformation for Tmax nor any ratio (relative) endpoint.
- [1]: AUC(0-t) if AUC(0-inf) cannot be derived
- [2]: If BID

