### 2.2. Study Objective(s) and Endpoint(s)

[figure not shown]
Objectives	Endpoints
Primary Objectives	Primary Endpoints

 
To evaluate the single dose PK profile of GSK2982772 from each test minitab Modified Release (MR) formulation in a capsule (120 mg) compared to the IR formulation (120 mg)
 
	
 
GSK2982772 area under the curve from time zero to infinity (AUC(0-inf)), area under the curve from time zero to the last measurable concentration AUC(0-t), area under the curve from time zero to 24 hours AUC(0-24), area under the curve from time zero to 12 hours AUC(0-12), maximum observed concentration (Cmax), Concentration at 12 hours post-dose (C12h), Concentration at 24 hours post-dose (C24h) and ratio of Cmax : C12h and Cmax : C24h, relative bioavailability (Frelformulation) based on AUC and Cmax
 

 
To evaluate the single dose PK profile of GSK2982772 from a (matrix monolithic) MR tablet (240mg) compared to the IR formulation (240mg).
 
	
 
GSK2982772 AUC(0-inf), AUC(0-t), AUC(0-24), AUC(0-12), Cmax, C12h, C24h, Cmax:C12h and Cmax:C24h, Frelformulation based on AUC and Cmax.
 

Secondary Objectives	Secondary Endpoints

 
To assess the impact of high fat meal on the PK of GSK2982772 following single dose
 
	
 
GSK2982772 AUC(0-inf), AUC(0-t), Cmax, time to Cmax (Tmax), FrelFE based on AUC and Cmax,
 

Objectives	Endpoints
administration of the selected minitab MR formulation in a capsule (120 mg)	

 
To determine if there are any dose dependant changes in the absorption of GSK2982772 following repeat dose administration of the selected minitab MR formulation in a capsule at target daily doses of 30, 60 and 240 mg
 
	
 
GSK2982772 AUC(0-24), Cmax, and Tmax if once daily (QD) dosing, on Day 1 and Day 3
 
GSK2982772 AUC(0-12), AUC(12-24), Cmax, and Tmax after morning dose, Cmax and Tmax after evening dose if twice daily (BID) dosing, on Day 1 and Day 3
 

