## 2.4. Statistical Hypotheses / Statistical Analyses

No formal hypothesis will be tested. However, point estimates and corresponding 90% confidence intervals will be derived for the ratio between each minitab MR formulation relative to the IR formulation for the geometric mean of Cmax, Cmin, C12, C24, peak-to-trough ratio, AUC(0-inf), AUC(0-12), and AUC(0-24). PK parameters at the 12 hour time point will only be included if BID dosing is used.

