#### 8.1.2. Summary Measure

For each release rate in Periods 1 through 3 of Part A, and Periods 1 and 2 of Part C, descriptive statistics (n, arithmetic mean, standard deviation [SD], 95% CI, minimum, median and maximum,) will be calculated by treatment for all PK concentrations over

time and for the derived PK parameters. In addition, for loge-transformed PK parameter variables geometric mean, 95% CI, and %CVb will be provided, where %CVb = (100 \*  $\sqrt{\exp(\text{SD}^2) - 1}$ ) and SD is the standard deviation of log-transformed data.

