**NOTES:**

- Additional parameters may be included as required.
- No log transformation for  $T_{\max}$  nor any ratio (relative) endpoint.
- [1]:  $AUC_{(0-t)}$  if  $AUC_{(0-\infty)}$  cannot be derived
- [2]: If BID formulation.
- [3]: QD formulation only.

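### The SAP plans a geometric-mean MR/IR comparison of the peak-to-trough ratio, yet bars the log scale for ratio endpoints and models neither ratio, so the interval planned for primary endpoint Cmax:C24h has no method

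*SAP*

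**What the plan says.** SAP 2.2 places the ratios among the primary endpoints: "Concentration at 24 hours post-dose (C24h) and ratio of Cmax : C12h and Cmax : C24h". SAP 2.4 plans point estimates and 90% confidence intervals for each minitab MR formulation against IR, "for the geometric mean of Cmax, Cmin, C12, C24, peak-to-trough ratio" and several AUCs. The same section adds that "PK parameters at the 12 hour time point will only be included if BID dosing is used", so Cmax:C24h is the one peak-to-trough ratio always in scope under the SAP.

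The parameter table in SAP 8.1.1.2 defines Cmax:C24h as "Ratio of maximum and 24 hour concentrations". The notes under that table say "No log transformation for Tmax nor any ratio (relative) endpoint", and the notes to 8.2.1.2 repeat the rule for the secondary parameters.

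SAP 8.1.2 provides, for every derived parameter, "descriptive statistics (n, arithmetic mean, standard deviation [SD], 95% CI, minimum, median and maximum,) will be calculated by treatment". It adds a geometric mean and %CVb only for log-transformed parameters. The mixed model in 8.1.5.1 is headed as log scale and lists the AUCs, Cmax, C12h if BID, and C24h.

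Protocol 10.1 plans 90% intervals for the peak-to-trough ratio of each minitab formulation relative to IR. Protocol 10.4.1 promises 90% intervals for Cmax:C12h and Cmax:C24h at 120 mg and 240 mg, which covers Parts A and C. It does not name a scale.

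**The concern.** A model-based confidence interval for a ratio of geometric means is a back-transformed difference on the log scale. One SAP section plans that analysis for the peak-to-trough ratio, another forbids the transformation it needs, and the model section leaves the endpoint out. A programmer following the SAP cannot produce the planned interval without overriding one of these sections, and the choice of scale stays open until the data have been seen.

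The scale matters because C24h after IR dosing is a very small denominator. The protocol gives a half-life of about 2 to 3 hours, so by 24 hours the IR concentration has fallen several hundred-fold from its peak. Modest differences in half-life then become large differences in Cmax:C24h, and a raw-scale mean is pulled by the participants with the shortest half-lives.

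**Working it through.** **1. The text, side by side**

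- SAP 2.4: MR/IR ratio of geometric means with 90% CI, including the peak-to-trough ratio. It names minitab MR only.
- SAP 8.1.1.2 notes: no log transformation of any ratio endpoint. The table they govern has two, Cmax:C12h (if BID) and Cmax:C24h.
- SAP 8.1.5.1: log-scale endpoint list without either ratio.
- SAP 8.1.2: geometric mean and %CVb for log-transformed parameters only. With the note in force, the ratios get n, arithmetic mean, SD, 95% CI, minimum, median and maximum.

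For Part A the SAP contradicts itself. For Part C the gap is between the SAP and Protocol 10.4.1.

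**2. What is lost**

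log(Cmax:C24h) = log Cmax − log C24h, and 8.1.5.1 already models both terms on the log scale. With the same participants in each mean,

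GMR(Cmax:C24h) = GMR(Cmax) / GMR(C24h).

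The point estimate is therefore recoverable from planned output. Its 90% CI is not, because that needs the within-participant covariance of the two terms, that is, a separate fit to the log ratio.

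**3. What the raw scale would cost**

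The documents state no precision for Cmax:C24h, so there is no planned figure to reproduce.

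Inputs from the documents: half-life about 2 to 3 h (Protocol 3.1); 12 completers (Protocol 10.2.1 and 10.2.3); between-subject CVs of 48.7% for AUC and 58.5% for Cmax in Part A (Protocol 10.2.3).

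Assumptions: mono-exponential decline; IR Tmax of 1 h; log-normal half-life around 2.5 h with CV 5 to 15%; MR ratio log-normal with CV 30 to 58.5%.

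IR ratio: Cmax:C24h = 2^((24 − Tmax)/half-life).

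- Half-life 3 h: 2^(23/3) = 203
- Half-life 2.5 h: 2^(23/2.5) = 588
- Half-life 2 h: 2^(23/2) = 2,896

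The range is 161 to 2,048 with Tmax 2 h, and 228 to 3,444 with Tmax 0.5 h.

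Simulated IR samples of 12, t-based 95% intervals:

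| Half-life CV | Arithmetic / geometric mean (typical sample) | Raw-scale coverage | Upper limit too low | Lower limit too high | Log-scale coverage |
|---|---|---|---|---|---|
| 5% | 1.04 | 93.6% | 5.5% | 0.9% | 95% |
| 10% | 1.19 | 88.6% | 11.2% | 0.2% | 95% |
| 15% | 1.49 | 78.3% | 21.7% | under 0.1% | 95% |

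Raw-scale coverage is for the arithmetic mean and log-scale coverage for the geometric mean. Almost all raw-scale misses are upper limits that are too low.

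At half-life CV 10% and 15% the two largest IR values supply 35% and 46% of the total, against 2/12 = 17% if all were equal. The sample median stays close to the geometric mean: 592 against 606 at CV 10%, and 590 against 626 at CV 15%.

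For MR, the arithmetic mean is only 4 to 13% above the geometric mean.

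For the MR/IR comparison (IR half-life CV 15%, MR ratio CV 58.5%, MR geometric mean of 5 assumed), the ratio of arithmetic means is typically 0.0059 and the ratio of geometric means 0.0080. The first is lower by 1 − 0.0059/0.0080 = 26%.

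**The case against.** Several points on the other side stand.

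- **The scale is not settled.** SAP 2.4 points to geometric means and the notes to 8.1.1.2 point away from them. A reader might infer that the primary result will be reported on a distorted scale; the documents support only that they conflict.
- **A robust summary is planned.** The median, minimum and maximum are reported, so only the arithmetic mean, SD and 95% CI are exposed.
- **The size rests on assumptions.** The 2 to 3 hours in the protocol is not described as a between-participant range, so the 14-fold span from 203 to 2,896 should not be read as an observed spread. At half-life CV 5% the loss is slight, and the effect falls mainly on IR.
- **The endpoint's weight is limited.** A reader might call Cmax:C24h the principal measure of a flatter profile. The documents list it among several primary endpoints, give once-daily convenience as the purpose and mention flatness as a possible advantage. No hypothesis is tested, and no quantitative stopping rule depends on it.
- **A clash within one table is not shown.** A reader might expect a raw-scale ratio beside the Cmax and C24h geometric mean ratios. The model results and the parameter summaries are separate displays.

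One defence does not stand. If the note's wording meant only relative bioavailability, it would conflict with 8.1.5.1, which obtains Frel by back-transforming a log-scale difference.

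**Conclusion.** The point holds as an inconsistency that leaves a primary endpoint without an analysis method. Under the SAP the always-included case is Cmax:C24h; Cmax:C12h is affected only if dosing is BID. The geometric-mean commitment in SAP 2.4 concerns minitab MR, so for Part C the shortfall is against Protocol 10.4.1.

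The numerical consequence is conditional. If the raw scale were used, the nominal 95% interval for the IR mean would cover about 94% down to 78% of the time with 12 participants, under the half-life spread, Tmax and mono-exponential decline assumed above. MR summaries would change modestly. It should be corrected before analysis, but it does not undermine the AUC, Cmax or C24h comparisons.

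**What to change.** - In the notes to SAP 8.1.1.2, limit the no-log rule to Tmax by removing "nor any ratio (relative) endpoint". Do the same in 8.2.1.2 for consistency; no geometric-mean commitment is breached there.
- Add log(Cmax:C24h), and log(Cmax:C12h) if BID, to the endpoint list in 8.1.5.1 for Parts A and C. Removing the phrase alone would not supply a model.
- Report geometric means, %CVb and MR/IR ratios with 90% CI for these endpoints, and extend SAP 2.4 to name the Part C tablet.
- State how a non-quantifiable C24h enters the ratio. SAP 10.5.2 assigns zero in concentration summaries, which would leave both the ratio and its log undefined. The documents give no quantification limit, and low C24h after IR is where this is most likely. Simply dropping those participants would remove the largest IR ratios, so the number affected should be reported.

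The cost is a few SAP text edits and one or two extra model fits, with no new data.

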#### 8.1.2. Summary Measure

For each release rate in Periods 1 through 3 of Part A, and Periods 1 and 2 of Part C, descriptive statistics (n, arithmetic mean, standard deviation [SD], 95% CI, minimum, median and maximum,) will be calculated by treatment for all PK concentrations over

time and for the derived PK parameters. In addition, for loge-transformed PK parameter variables geometric mean, 95% CI, and %CVb will be provided, where %CVb = (100 \*  $\sqrt{\exp(\text{SD}^2) - 1}$ ) and SD is the standard deviation of log-transformed data.

### 8.1.3. Population of Interest

The primary pharmacokinetic analyses will be based on the Pharmacokinetic population, unless otherwise specified.

### 8.1.4. Strategy for Intercurrent (Post-Randomization) Events

- Participant study completion (i.e. as specified in the protocol) was defined as completing all phases of the study including the follow-up visit.
- Withdrawn participants may be replaced in the study. Replacement participants enrolled will be dosed with the next planned treatment of the withdrawn participant, and they will not receive any treatment that the withdrawn participant has already received with the exception of the need to increase participant numbers to obtain the minimum number of evaluable participants required for interim decisions, and to obtain data in any other treatment that is required for a valid comparison. Replacement participants will receive the required treatments in the same order as planned for the original participant and the minimum washout period will be respected with regard to the timing of dosing of the IR formulation.
- All available data from participants who were withdrawn from the study will be listed and all available planned data will be included in summary tables and figures, unless otherwise specified.

### 8.1.5. Statistical Analyses / Methods

Details of the planned displays are provided in [Appendix 11: List of Data Displays](#) and will be based on GSK Data Standards and statistical principles.

Unless otherwise specified, endpoints / variables defined in Section [8.1.1](#) will be summarised using descriptive statistics, graphically presented (where appropriate) and listed.

#### 8.1.5.1. Statistical Methodology Specification

The following pharmacokinetic statistical analyses will only be performed if sufficient data is available (i.e. if participants have well defined plasma profiles).

Endpoint (log scale)

 
• AUC(0-inf)
 
• AUC(0-t) if AUC(0-inf) cannot be derived
 
• AUC(0-12) if BID
 
• AUC(0-24h)
 

 
• <math>C_{\max}</math>
 
• <math>C_{12h}</math> if BID
 
• <math>C_{24h}</math>
 

Model Specification

 
• For each endpoint a mixed model will be fit with 3 observations per participant expected in Part A, and 2 observations per participant in Part C. The model will contain formulation as a fixed, categorical effect, and a random intercept for subject.
 
• The Kenward and Roger method for approximating the denominator degrees of freedom and correcting for bias in the estimated variance-covariance of the fixed effects will be used.
 

Model Checking & Diagnostics

 
• Model assumptions will be applied, but appropriate adjustments may be made based on the data.
 
• In the event the model fails to converge, the RANDOM statement will be removed and alternative covariance structures such as CS, CSH, or UN for the R matrix will be used by specifying 'type=' on the REPEATED line. Akaike's Information Criteria (AIC) will be used to assist with the selection of covariance structure.
 
• Distributional assumptions underlying the model used for analysis will be examined by obtaining a normal probability plot of the residuals and a plot of the residuals versus the fitted values (i.e. checking the normality assumption and constant variance assumption of the model respectively) to gain confidence that the model assumptions are reasonable.
 
• If there are any departures from the distributional assumptions, alternative models will be explored using appropriate transformed data.
 
• If outliers are detected, an additional table will be produced with outlying observations omitted.
 

Model Results Presentation

 
• Point estimates and corresponding 90% CI will be computed for the differences in the endpoint for each GSK2982772 MR formulation vs GSK2982772 IR formulation.
 
• The relative bioavailability ratio, <math>F_{rel,formulation}</math>, and 90% CI will be calculated by back-transforming the difference between the least square means for each of the two formulation comparisons. See Section 10.6.4
 

## 8.2. Secondary Pharmacokinetic Analyses - Part A (Periods 4-6), Part B, and Part C (Periods 3-6)

### 8.2.1. Endpoint / Variables

#### 8.2.1.1. Drug Concentration Measures

Refer to [Appendix 5](#): Data Display Standards & Handling Conventions (Section [10.5.2](#) Reporting Standards for Pharmacokinetic)

### 8.2.1.2. Derived Pharmacokinetic Parameters

Pharmacokinetic parameters will be calculated by standard non-compartmental analysis according to current working practices and using the currently supported version of WinNonlin. All calculations of non-compartmental parameters will be based on actual sampling times. Pharmacokinetic parameters listed will be determined from the plasma concentration-time data, as data permits.

Parameter	Parameter Description
Part A - Food Effect	
$AUC_{(0-\infty)}$	Area under the curve from time zero to infinity
$AUC_{(0-t)}^1$	Area under the curve from time zero to last quantifiable concentration
$AUC_{(0-12)}^2$	Area under the curve from time zero to 12 hours
$AUC_{(0-24)}^3$	Area under the curve from time zero to 24 hours
$C_{max}$	Maximum observed concentration
$C_{12h}^2$	Concentration at 12 hours post-dose
$C_{24h}$	Concentration at 24 hours post-dose
$C_{max}:C_{12h}^2$	Ratio of maximum and 12 hour concentrations
$C_{max}:C_{24h}$	Ratio of maximum and 24 hour concentrations
$T_{max}$	Time of maximum observed concentration
Part B – Repeat Dose	
$AUC_{(0-12)}^2$	Area under the curve from time zero to 12 hours
$AUC_{(12-24)}^2$	Area under the curve from time 12 hours to 24 hours
$AUC_{(0-24)}^3$	Area under the curve from time zero to 24 hours
$C_{max}$	Maximum observed concentration
$C_{12h}^2$	Concentration at 12 hours post-dose
$C_{24h}$	Concentration at 24 hours post-dose
$C_{max}:C_{12h}^2$	Ratio of maximum and 12 hour concentrations
$C_{max}:C_{24h}$	Ratio of maximum and 24 hour concentrations
$T_{max}$	Time of maximum observed concentration
Part C – High Dose Food Effect	
$AUC_{(0-\infty)}$	Area under the curve from time zero to infinity
$AUC_{(0-t)}^1$	Area under the curve from time zero to the last quantifiable concentration
$AUC_{(0-24)}^3$	Area under the curve from time zero to 24 hours
$AUC_{(0-12)}^1$	Area under the curve from time zero to 12 hours
$T_{max}$	Time of maximum observed concentration
$C_{max}$	Maximum observed concentration
$C_{min}$	Minimum observed concentration
$C_{24h}$	Concentration at 24 hours post-dose
$C_{12h}^2$	Concentration at 12 hours post-dose

Parameter	Parameter Description
$C_{\max}:C_{12h}^2$	Ratio of maximum and 12 hour concentrations
$C_{\max}:C_{24h}$	Ratio of maximum and 24 hour concentrations

